## Study hypothesis

No difference between 5 and 10 units of intravenous regular insulin in lowering potassium levels in patients with hyperkalemia at 2 hours.

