### **Sampling and sample size**

Our target will be all patients with hyperkalemia presenting to the emergency departments in both hospitals. The Sample size was calculated based on a study published in Critical Care Explorations Journal 2020 with the article named *Comparison of IV Insulin Dosing Strategies for Hyperkalemia in the Emergency Department* by **Kayvan Moussavi** et al (8). The anticipated effect size  $d = 0.2$  with alpha error prob = 0.0250 (one-side), actual power 90, Standard deviation of 0.62 and allocation ratio 1:1. The calculated sample size is 320 (160 in each arm). Our statistician estimated a 5% drop rate. So the sample size increased to 336 (168 in each arm).

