## Planned interim analyses.

Interim analyses will be done after collecting 50% of the data.

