## **25. Anticipated results**

The antihyperkalemic measure effect of intravenous regular insulin 5units is not inferior to intravenous regular insulin 10 units and there will be fewer side effects.

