5 versus 10 units of insulin in hyperkalemia management: multi-center, prospective, double blinded, non-inferiority, randomized control trial in adult patients with age of 18 years and more at two emergency departments Sultan Qaboos university hospital and Royal hospital. We will include patients with potassium level 5.5 mEq/l and more. We will measure the mean reduction of insulin level among both groups at 2 hours from treatment. Written consent will be obtained from all patients. Eligible subjects will be enrolled. Control group will receive 10 units intravenous insulin with Dextrose 50 % 50 ml over 15 minutes and Salbutamol nebulization. Intervention group will receive 5 units intravenous insulin with Dextrose 50 % 50 ml over 15 minutes and Salbutamol nebulization. Patient will be monitored and basic labs will be recorded. Blood sugar will be monitored at 0, 60 and 120 (2 hours) minutes. Potassium level will be measured at presentation and at 120 minutes (2 hours) from insulin administration.

Sample size calculation

We aim to study all hyperkalemia patients who come to the emergency departments of both hospitals. The sample size determination was influenced by a 2020 article in the Critical Care Explorations Journal titled "Comparison of IV Insulin Dosing Strategies for Hyperkalemia in the Emergency Department" authored by Kayvan Moussavi and colleagues. We expect an effect size of $d=0.2$, with an alpha error probability of 0.0250 (one-sided), a true power of 90, a standard deviation of 0.62, and a 1:1 allocation ratio. The sample size deduced is 320, split evenly between both groups. Anticipating a 5% attrition rate, we've adjusted our total sample to 336 participants, with 168 in each group

Aims and objectives

The aim of this study is to compare the efficacy of two insulin doses (5 units and 10 units) in reducing serum potassium level in patients receiving hyperkalemia treatment.

Outcomes

Primary outcome

- To study the efficacy of two intravenous insulin doses (5 units and 10 units) in reducing serum potassium level in patients receiving hyperkalemia treatment using the main laboratory measurements. (the aim of reduction of 0.6 mmol/l +/- 0.2 mmol/L) (1). Blood sample will be collected and send to the main laboratory for analysis at two hours from medications administration. The efficacy of the 2 doses will be measured at 2 hours from administration of medications by comparing the amount of changes in potassium level at two hours.

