Secondary outcomes

1. Study the mean difference of the response to the anti-hyperkalemic measures based on the level of initial potassium (serum potassium before given any medications – At baseline) (the investigators will categorize potassium level into groups mild (5.5–6 mmol/l), moderate (6–6.5 mmol/l) and severe (>6.5 mmol/l) and will see the mean difference in reduction in potassium level in between the 2 doses).
2. Association of mean potassium reduction with initial blood sugar level (blood sugar level before given any medications – At Baseline) on potassium reduction (the investigators will categorize blood sugar into groups: Below 10mmol/L, 10.1-14.9 mmol/L, and 15 – 19.9mmol/L among each group the investigators will see the mean potassium reduction level).
3. Incidence of hypoglycemia (random blood sugar (RBS) \leq 3.89 mmol/l in Diabetic patients and less than 3 mmol/l in non-Diabetic patients) (12). (and risk factor Characteristic of patients of higher risk of developing hypoglycemia (the investigators will investigate which group of patients will have a high risk of hypoglycemia ((e.g: initial Glucose level, initial creatinin/renal function, comorbidities, type of dialysis...)).

Safety outcomes

Adverse events are reported at each visit.

Populations

Intention-to-treat (ITT)

All randomized study subjects. This will be seen as the primary population for the analysis.

Per Protocol (PP)

All randomized study subjects completing the whole study period (complete cases). For a specific analysis, study subjects with missing data on any of the variables in the model will be excluded from the analysis. Analyses of this population is seen as a sensitivity analysis to investigate whether conclusions are sensitive to assumptions regarding the pattern of missing data.

Statistical analysis

Primary outcome

The data analysis for the clinical trial will be conducted using IBM SPSS Statistics version 29.0. Categorized variables will be presented as percentages, and continuous variables will be presented as means with standard deviations or medians with interquartile ranges. The primary outcome, the reduction in serum potassium levels, will be analyzed using a linear mixed effect model that adjusts for baseline potassium levels. A p-value of <0.05 will be considered statistically significant.

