The intention-to-treat (ITT) analysis will include all subjects who provide at least one post-baseline valid measurement. The per-protocol (PP) analysis will only include subjects who have completed the study according to the protocol and who have valid measurements for all time points. Non-inferiority will be concluded if both the ITT and PP analyses show that the difference in means between the two treatment groups is not statistically significant and lies above the margin of -20 units.

Secondary outcomes

Normally distributed continuous variables will be compared between the groups using Independent 't' test or else with Mann-Whitney 'U' test and categorized levels will be compared using chi-square test. The incidence of hypoglycemia will be presented using percentage with 95% confidence interval. A p-value of <0.05 will be considered as statistical significance.

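### The SAP's non-inferiority rule rests on a non-significant difference and an undefined margin of −20 units, so it is not a non-inferiority test

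*SAP*

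**What the plan says.** Both documents call the trial a non-inferiority trial. The rule that decides it appears once, in the SAP under Statistical analysis, Primary outcome. Non-inferiority is concluded if, in both the ITT and PP analyses, "the difference in means between the two treatment groups is not statistically significant and lies above the margin of -20 units". The same section sets the significance level: "A p-value of <0.05 will be considered statistically significant". It does not say whether that is one- or two-sided.

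Neither document defines the units, gives a margin in mmol/L, states which arm is subtracted from which, or compares a confidence limit with a margin. The outcome is on a mmol/L scale ("the aim of reduction of 0.6 mmol/l +/- 0.2 mmol/L"). The sample size uses an effect size of 0.2 "with alpha error prob = 0.0250 (one-side), actual power 90, Standard deviation of 0.62", and does not call the 0.2 a margin. The Protocol's study hypothesis is "No difference between 5 and 10 units of intravenous regular insulin in lowering potassium levels". Its anticipated result is that the effect of 5 units "is not inferior to intravenous regular insulin 10 units and there will be fewer side effects". Neither statement mentions a margin.

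**The concern.** A non-inferiority claim needs evidence that excludes a deficit as large as a stated margin. That evidence is a confidence limit lying on the right side of the margin. This rule asks for something else.

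- **Non-significance is made a condition for success.** Failing to detect a difference is not evidence that a difference is small, and the condition becomes easier to meet as the data become noisier or fewer. With a two-sided test it also refuses the claim when 5 units is significantly better.
- **The margin clause cannot do its job.** On the outcome's own scale −20 is out of reach, and the clause is applied to the difference, not to a confidence limit.

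This one sentence decides the trial's conclusion. If it does not control the chance of calling a worse dose non-inferior, the one-sided 2.5% in the sample-size section is not the error rate the trial will have.

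**Working it through.** **Inputs.** SD 0.62, 160 evaluable per arm (168 enrolled), 1:1 allocation, one-sided alpha 0.025, 90% power and effect size 0.2 (Protocol, Sampling and sample size; SAP, Sample size calculation). Significance at p<0.05 (SAP). Target reduction 0.6 mmol/L (both documents).

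**Assumptions.** The 0.2 is read as 0.2 mmol/L and as the intended margin. The p-value is two-sided. D is the mean reduction with 5 units minus that with 10 units. Normal approximation.

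**The plan's own figure.** n per arm = 2 × (0.62/0.2)² × (1.96 + 1.2816)² = 202, so 404 in total. The stated 320 is not reproduced. The loss adjustment is: 320 × 1.05 = 336.

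**Can −20 bind?** 20/0.62 ≈ 32 SDs, and 20/0.6 ≈ 33 times the target reduction. It cannot.

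**Can −0.20 on the difference bind?** SE = 0.62 × √(2/160) = 0.0693, and 1.96 × SE = 0.136. Non-significance already forces D > −0.136, so D > −0.20 follows automatically. The clause would bind only if 1.96 × SD × √(2/160) > 0.20, that is, SD > 0.913.

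**Chance of declaring non-inferiority.** Under the SAP rule it is P(|D̂| < 1.96 × SE). Under a confidence-interval rule it is P(D̂ − 1.96 × SE > −0.2). At 160 per arm and SD 0.62:

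| True D (mmol/L) | SAP rule | CI rule, M = 0.2 |
|---|---|---|
| −0.2 | 17.7% | 2.5% |
| −0.1 | 69.7% | 30.2% |
| 0 | 95.0% | 82.3% |
| +0.1 | 69.7% | 99.1% |
| +0.2 | 17.7% | >99.9% |

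**Dependence on sample size.** At true D = −0.2 and SD 0.62, the SAP rule passes 76.1% of the time at 30 per arm, 63.6% at 50, 37.4% at 100, 17.7% at 160 and 10.0% at 202. Losing patients helps the claim.

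**Dependence on residual SD.** At true D = −0.2 and 160 per arm:

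| SD | 0.40 | 0.50 | 0.62 | 0.80 | 1.00 |
|---|---|---|---|---|---|
| SAP rule passes | 0.6% | 5.3% | 17.7% | 39% | 57% |

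The rate equals 2.5% only where 2 × 1.96 × SD × √(2/160) = 0.2, that is, SD = 0.456.

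**Requiring both populations.** In a simulation with PP a subset of ITT and 8 per arm smaller (1,000,000 runs), the 17.7% becomes 14.5% for 168/160 per arm and 16.3% for 160/152.

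**Other readings at SD 0.62 and 160 per arm.**
- If 0.2 is in SD units, the margin is 0.2 × 0.62 = 0.124 mmol/L, and a dose worse by 0.124 passes 57% of the time.
- If −20 means 20% of the 0.6 target, the clause is −0.12 on the point estimate. It then binds, since −0.12 is above −0.136. A dose worse by 0.12 passes about 50% of the time (59% without the clause), and one worse by 0.2 passes 12.4% of the time.

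**Power of a correct rule.** Φ(0.2/0.0693 − 1.96) = Φ(0.925) = 82.3%. If both populations must pass, simulation gives 78.7% (160/152) to 80.9% (168/160). With M = 0.124, power is Φ(1.789 − 1.96) = 43%.

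**The case against.** The strongest defence is that the sentence is loosely worded. If it means that the lower 95% confidence limit must lie above −0.20 mmol/L, then with non-significance added D̂ must fall between −0.2 + 0.136 = −0.064 and +0.136. False non-inferiority at D = −0.2 is then 2.5%, as planned, and power at no difference is about 80%. This reading is not in the text, which names no confidence limit and says −20. Even so, it repairs only half the rule: a significantly better 5-unit arm would still fail.

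Second, sidedness is not stated. If significance is tested one-sided towards inferiority, a better 5-unit arm is not blocked, and at one-sided p<0.05 the false non-inferiority rate at −0.2 is Φ(1.645 − 2.885) = 10.7%. The blocking point therefore depends on a two-sided test, which is how an unqualified p<0.05 is usually taken. Nor do the documents anticipate an advantage for 5 units in potassium lowering, so the risk of passing a worse dose matters more in practice.

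Third, the 17.7% rests on a margin that the documents never name, and on SD 0.62 although the SAP adjusts for baseline. Below a residual SD of 0.456 the rule is stricter than 2.5%. This stands: 17.7% is an illustration, not an established error rate. It does not rescue the rule, because an error rate that moves from 0.6% to 57% with the SD is not controlled by a margin.

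Fourth, the SAP disagrees with itself on populations. Its Populations section makes ITT primary (all randomised) and PP a sensitivity analysis. Its Primary outcome section requires both to pass and limits ITT to patients with a post-baseline value. Any replacement rule must settle this.

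**Conclusion.** The rule is wrong as written. It makes non-significance a requirement for non-inferiority, and its margin has no defined scale and has no effect at −20 mmol/L or at −0.20 on the difference. If M = 0.2 mmol/L, SD 0.62, 160 per arm and two-sided p<0.05, a dose worse by the margin passes 17.7% of the time (14.5–16.3% when both populations must pass) against the planned 2.5%. A dose better by 0.2 is refused about 82% of the time. The exact size depends on those assumptions. That the error rate is set by precision and not by a margin holds for the sentence as written, whichever SD applies. This must be fixed before analysis.

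**What to change.** Delete the non-significance condition and the −20 units. Replace them with a rule of this form: non-inferiority is concluded only if, in both the ITT and PP analyses, the lower limit of the two-sided 95% CI for the baseline-adjusted difference in mean potassium reduction (5 units minus 10 units) lies above −M mmol/L.

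Along with that:
- State M in mmol/L with its justification, in both the Protocol and the SAP. Use 0.2 only if the team confirms that the sample size intended it.
- Restate the study hypothesis in terms of M.
- Reconcile the SAP's two descriptions of ITT and of the role of PP, so that the rule can be applied.
- Say that the rule is not applied at the interim look. The Protocol says only that "Interim analyses will be done after collecting 50% of the data", without giving a purpose.

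The change is one of wording, but its effect on power must be disclosed. With M = 0.2, SD 0.62 and 160 per arm, power is about 82% (79–81% if both populations must pass), not 90%. Reaching 90% needs about 202 per arm: 404 evaluable, or 404/0.95 ≈ 426 with 5% loss. Alternatively, it needs a residual SD after baseline adjustment of at most 0.2/(3.2416 × √(2/160)) ≈ 0.55. If M were 0.124, power at 160 per arm would be about 43%. When the doses are truly equal, the claim becomes harder to reach than under the present rule (82.3% against 95.0%).

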## 1. Summary:

**Introduction:** Hyperkalemia is a serum Potassium (K) level of more than 5.5 mEq/L. It is a common emergency medicine presentation and can be life-threatening. Because of the emergency in correcting hyperkalemia, different medications are used to reduce high potassium levels to normal as soon as possible. Salbutamol inhalers, Glucose solutions, and Insulin are the main medications for managing hyperkalemia. Insulin and Dextrose shift potassium ions into body cells by stimulating the sodium/potassium ATP pump. Its effect starts in less than fifteen minutes and can last up to sixty minutes. It usually reduces potassium up to 1.1 mEq/l. There are different recommendations for Insulin dose and rate of administration for patients with hyperkalemia.

**Method:** This will be a multi-center, prospective, double-blind, non-inferiority, randomized control trial. 336 hyperkalemia patients will be randomized to the intervention group 5 units of intravenous Regular insulin and 10 units of intravenous insulin groups with fifty ml of Dextrose Fifty percent. They will be enrolled once their potassium level is 5.5mEq/L or more. The attending physician/ investigator and patient will be blinded about the dose of insulin that the patient received. Serum potassium will be measured at 0 and at 120 minutes from the start of the medications. Random blood glucose will be measured at 0, 60, and 120 minutes by Glucometer. The safety of our patients will be assessed by documentation of all adverse events, vital signs, and clinical assessment before and after drug administration. The study will end at 2 hours from insulin administration.

**Aim:** Our research idea aims to compare two recommended doses of Insulin (5 Units vs. 10 Units of Regular insulin given intravenously over thirty minutes) in the management of patients with hyperkalemia.

**Primary objective:** Mean reduction in serum potassium level using the main laboratory results at two hours from medication administration.

**Secondary objectives:** effect of initial (baseline) potassium level on the mean potassium reduction, and frequency of hypoglycemia between the 2 groups. Does the initial (baseline) blood glucose level will affect the function of insulin/dextrose in lowering potassium levels?

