## **11. Ethical considerations**

Ethical approval will be needed from both hospitals before starting our research. Any adjustment advised by all ethical committees the research team will apply it to ensure patient safety. At any time during our study if the investigator noticed any increase risk on the patient safety the investigator will stop our study protocol.

Because the study will not deviate from what is practiced by some physician and what is recommended by some guidelines our researchers team do not anticipate major harm on the patients. Even with this our investigator will follow our patients/participants and will stop the study if any indicator for harm rose at any time of the study. Our study will help if it proved no difference in the effect of both doses in 2 main things. The 1st one less hypoglycemia for the patients in the future and the 2nd main point cost effect as less doses of the same medication will be required to achieve the same goal.

By the end of the study all participants will be contacted and our investigators will share the results with them and how their contribution helped the advancement of medical field.

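### The SAP plans no between-dose effect estimate with a confidence interval for hypoglycaemia, and its unadjusted comparison leaves out diabetes status and baseline glucose

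*SAP*

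**What the plan says.** The protocol Summary lists as a secondary objective the "frequency of hypoglycemia between the 2 groups". The SAP repeats hypoglycaemia as its third secondary outcome, with a cut-off that depends on diabetes: at or below 3.89 "mmol/l in Diabetic patients and less than 3 mmol/l in non-Diabetic patients".

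The analysis is given in the last paragraph of the SAP, first for categorical outcomes and then for this outcome in particular: "categorized levels will be compared using chi-square test. The incidence of hypoglycemia will be presented using percentage with 95% confidence interval". The decision threshold is "A p-value of <0.05 will be considered as statistical significance". No risk difference, risk ratio or odds ratio between doses is named, and no covariates enter the comparison. The SAP also plans to look for risk factors for hypoglycaemia, including initial glucose and comorbidities, but as a separate question from the dose comparison.

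The protocol relies on this outcome in several places. Section 2 (The gap in the studies) bases the case for 5 units on similar potassium lowering with fewer hypoglycaemic events. Section 11 gives "less hypoglycemia for the patients in the future" as the first of two benefits. Section 25 expects that 5 units "is not inferior to intravenous regular insulin 10 units and there will be fewer side effects".

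**The concern.** The trial's argument has two halves: potassium falls about as much with 5 units, and hypoglycaemia is less frequent. The first half has a model, a margin and a sample size. The second has a significance test and an interval attached to an incidence, which may be per arm or pooled. Neither output states how large a reduction, or increase, in hypoglycaemia remains compatible with the data.

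That matters because the sample size was set on potassium alone. If events are uncommon, the likely result is a non-significant test, and such a result can arise both when 5 units does nothing for hypoglycaemia and when it halves it.

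A smaller issue is efficiency. Diabetes status sets the event cut-off, and the SAP itself names initial glucose as a possible risk factor. DM type and 0-minute blood sugar are on the data collection sheet. The SAP adjusts the potassium analysis for baseline potassium but makes no matching use of baseline data here.

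**Working it through.** **Inputs.** From the SAP: 160 analysable patients per arm (168 enrolled), 1:1 allocation, p<0.05, taken as two-sided because the test is a chi-square. Neither document gives a hypoglycaemia rate, a target reduction or a power figure for it, so there is no plan figure to reproduce. The 10-unit rate is therefore an assumption, shown as a range, and the effect examined is a halving. (The 320 was derived for potassium; whether its stated inputs yield 320 is a separate matter. Here it is taken as given.)

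**Power.** With p the 10-unit rate, q = p/2, m = (p+q)/2 and n = 160:

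- null SE: s0 = √[2m(1−m)/n]
- alternative SE: s1 = √[(p(1−p)+q(1−q))/n]
- power = Φ[(p−q−1.96·s0)/s1]
- approximate CI half-width for the difference = 1.96·s1

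For 10% against 5%: m = 0.075, s0 = 0.02945, s1 = 0.02932. Power = Φ[(0.05−0.05772)/0.02932] = Φ(−0.263) = 0.396, and the half-width is 5.7 points.

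| Assumed rates, 10 vs 5 units | Expected events, both arms | Power | CI half-width (points) |
|---|---|---|---|
| 4% vs 2% | 9.6 | 18% | 3.7 |
| 6% vs 3% | 14.4 | 25% | 4.5 |
| 10% vs 5% | 24 | 40% | 5.7 |
| 15% vs 7.5% | 36 | 56% | 6.9 |
| 20% vs 10% | 48 | 71% | 7.7 |
| 25% vs 12.5% | 60 | 82% | 8.4 |

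Power crosses 50% at a 10-unit rate of about 13% and 80% at about 24%. Exact enumeration of the Pearson test agrees within about 2 points. With Yates' correction the 50% crossing moves to about 15%. With 168 per arm it is about 12%.

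**What an effect estimate would add.** Illustrative counts at 160 per arm, with Wilson intervals per arm and Newcombe intervals for the difference:

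- *16 vs 8 events.* Chi-square = 2.88, p = 0.09. Per-arm intervals are 6.2% to 15.6% and 2.6% to 9.6%. The risk difference is −5.0 points (−11.1 to +0.9). The p-value says only that the result is not significant; the interval shows that a large reduction is still plausible and that an increase beyond about 1 point is not.
- *24 vs 12 events.* Chi-square = 4.51, p = 0.03. Per-arm intervals are 10.3% to 21.3% and 4.3% to 12.7%, and they overlap. The risk difference is −7.5 points (−14.6 to −0.5), which excludes zero. Per-arm intervals are thus a poor guide to the contrast.

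**Covariates.** If half the patients are diabetic (assumed), the between-arm difference in diabetic share has SD √(2×0.25/168) = 0.055, or 5.5 points. If event rates differ by 10 points between diabetic and non-diabetic patients (assumed), that moves the contrast by 0.055 × 10 = 0.55 points, against an SE of 2.9 points at 10% vs 5%. In simulations of 1,500 trials at 16% vs 8%, adjustment for diabetes and glucose raised power from 61% to 67% when glucose was strongly prognostic, and from 63% to 64% when it was weaker. A separate simulation gave gains of 1 to 5 points with type I error held at about 5%.

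**The case against.** Hypoglycaemia is a secondary outcome, and the SAP's stated aim is potassium efficacy. The protocol passages on fewer side effects are expectation and ethical justification, not decision rules. Randomisation makes the unadjusted chi-square valid, and chance imbalance in diabetes is already part of its standard error. If the planned intervals are per arm, anyone can compute a risk difference from the two percentages and arm sizes. All of this stands, and it limits the point to a modest improvement.

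Several stronger readings are tempting and are not supported:

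- *A real halving would usually be missed.* This is true only if the 10-unit rate is below about 13%. At 15% to 20% a halving would more often than not be significant, and the documents give no rate.
- *A non-significant result will be reported as no difference.* The SAP does not say this for hypoglycaemia. Its rule that counts non-significance towards the conclusion is confined to the primary outcome.
- *The chi-square causes the low power.* It does not. At 16 vs 8 events the risk-difference interval also crosses zero.
- *Imbalance in diabetes biases the comparison.* It adds noise, and on the assumptions above not much.

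What the objection does not answer is that a contrast readers must reconstruct is not a pre-specified analysis, and the SAP leaves open which percentage its interval belongs to.

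**Conclusion.** The point holds in a limited form. The SAP pre-specifies no between-dose effect estimate with an interval for the outcome that carries the benefit side of the argument, and it leaves two relevant, already collected baseline variables out of the comparison. The first is the main defect; the second is an inexpensive gain in precision.

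How much the p-value alone would conceal depends on an event rate that the documents do not supply. The power range above assumes a halving, 160 analysable patients per arm and a two-sided 5% test. The covariate gain of about 1 to 6 points rests on assumed glucose effects. The trial is not invalid on this count, and the planned test is not wrong. It is a poor sole basis for judging benefit if events turn out to be uncommon.

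**What to change.** In the SAP, Secondary outcomes:

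1. Make the main hypoglycaemia comparison the 5-unit minus 10-unit risk difference with its 95% CI, from a logistic model with dose, diabetes status and 0-minute glucose, standardised to the trial population.
2. Pre-specify a threshold on total events, assessed blind to arm, below which the Mantel-Haenszel risk difference stratified by diabetes is used instead. This is needed because only about 10 events in total are expected at 4% vs 2%, too few for a stable model. Fixing the threshold in advance stops the estimator being chosen after the results are seen.
3. Report the event count and percentage in each arm, and say explicitly which percentage each interval belongs to.
4. Keep the chi-square as supportive, and state that the interpretation rests on the interval for the difference, not on whether p falls below 0.05.

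The cost is some SAP wording and a little analysis code; no new data are needed. Check that the standardised estimate can be produced in the named software (SPSS 29), or name another package. The downside is a model that becomes fragile when events are few, which step 2 addresses. More power would need more patients: 80% power for a halving takes 435 per arm at an assumed 10-unit rate of 10%, and 199 per arm at 20%.
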